## **1. Purpose of the Study and Background**

### **1.1 Purpose of the Study**

The primary aims of this study are to assess the feasibility, acceptability, and tolerability of a virtual reality (VR) behavioral activation (BA) treatment for individuals diagnosed with major depressive disorder (MDD). The secondary aim of this study is to explore the efficacy of using VR to deliver BA therapy to a clinical MDD population.

The primary hypothesis of this study is that VR is an acceptable, feasible, and safe way to deliver a BA intervention for individuals diagnosed with MDD. Acceptability will measure the participant's desire to continue using the VR treatment after the study ends, the participant's satisfaction with the VR treatment, the participant's use of the headset, and the participant's acceptance of VR treatment. Feasibility will look at how well VR can integrate into the BA therapy. Tolerability will measure simulator sickness and agitation while using the VR headset.

A secondary hypothesis is that VRBA will have stronger effects than BA treatment as usual or a waitlist control in treating individuals with MDD due to increased homework compliance. This is due to the research that has illustrated that homework compliance is one of the strongest predictors of treatment outcomes for BA. This hypothesis will be assessed by running t-tests comparing the change in PHQ-9 scores at timepoints across the three study arms.

This study will also comment on the following questions: Can one successfully deliver BA without the movement component, simulating just the experience of pleasure/ mastery? Does VRBA lead people to want to engage in real-life activities? Is the active ingredient of BA emotion or movement? Movement during the VRBA will be measured with the headset.

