## **3. Methods and Procedures**

### **3.1 Procedure**

Participants will be recruited from the clinic waitlist or through the study flyer. A total of 30 participants will be recruited, about 10 participants per study arm. These participants will be given the contact information of the protocol director. Upon reaching out to the protocol director, an informational phone script will be read to determine study eligibility and subject interest.

If subjects are interested and present with symptoms of depression, they will be invited to Stanford School of Medicine, Department of Psychiatry & Behavioral Sciences for an intake session. This session will include obtaining informed consent, the Mini International Neuropsychiatric Interview, and completing the demographic questionnaire. If subjects meet study eligibility, they will be randomized into either the VRBA, BA treatment as usual, or waitlist control arm of the study using 5 opaque, concealed envelopes in sets of 6 to preserve balance throughout the study. Participants will have a 1 in 3 chance of being randomized into each group. Participants will then be scheduled for their first treatment appointment.

The VR intervention will follow the protocol for Behavioral Activation (BA). Participants in the BA treatment as usual or VRBA arms of the study will meet with their clinician once per week for 50 minutes to receive BA therapy. These participants will complete the PHQ-9 at the

beginning of each session. If item 9 is endorsed, a risk assessment will be completed in real-time and appropriate actions will be taken.

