#### **4. Data Safety Monitoring Plan**

As this is a case series within standard of care procedures, steps to minimize risks to the confidentiality of identifiable information will be taken as with all HIPPA compliant services delivered at the Clinic. Data will all be labeled with the participants' assigned ID number. Protected Health Information will be kept separate from data and ID numbers in a Stanford University School of Medicine encrypted database to which only the PI and research assistants will have access. Psychological effects of study participation or breeches in confidentiality will be monitored and discussed at research meetings. There is a slight risk of motion sickness so participants will be closely monitored while immersed in the virtual scene, and if there is any discomfort they will be removed from the virtual environment. Participants are free to discontinue participation at any time. Any situation requiring medical attention will be promptly provided.

Given that participants enrolled are clinically depressed, suicidal ideation will be assessed each session. If it is revealed that a participant is expressing suicidal ideation, the clinician will conduct a thorough risk assessment in real time and a safety plan will be created. If it is determined the participant is an imminent danger to themselves, the clinician will initiate a 5150 hold and walk the participant to the hospital.

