# **Virtual Reality Behavioral Activation: An Intervention for Major Depressive Disorder**

**NCT04268316**

**April 13, 2021**

**Aim 1:** To evaluate whether using VR to administer a brief BA protocol is a feasible, acceptable, and tolerable treatment for individuals diagnosed with MDD.

**Aim 1 Analysis:** The feasibility, or degree to which VR could successfully be integrated into the brief BA protocol, was measured by commenting on qualitative barriers to use observed. Barriers were assessed by rates of dropout, adverse events, the number of times the headset was used, and the level of presence experienced in the headset, all of which were represented in a table, as recommended by Birkhead et al. (2019). Level of presence was obtained by participant report from a Likert scale of 0 (not at all) through 4 (very strongly) for each question; and with three questions, there was a possibility of yielding a score between 0 and 12. The average total presence for each participant, intend-to-treat (ITT) participants, and protocol completers were then calculated and placed into a table. The average presence experienced was also calculated as a percentage by dividing the average score by 12 (the maximum score). Acceptability of the VR BA treatment was measured by participant report using the TAM, with the agreeance choice on the Likert scale represented from 0 (strongly disagree) through 4 (strongly agree). The number of questions in each category determined the outcome range (either 0-12 for three questions or 0-16 for four questions). Each participant's scores were then averaged and placed into a table, along with the average ITT participants and protocol completers' scores. The average percentage of acceptance was also calculated by dividing the average score by the maximum score in the outcome range. In order to determine the degree of

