**Aim 2 Analysis:** In order to determine any initial clinical efficacy of the VR BA treatment compared to BA treatment as usual and a waitlist control, participants' depression scores were measured using the PHQ-9 at four time points. With the goal of randomizing 30 participants, the average change between PHQ-9 scores at time 4 and time 1 for each of the three groups were going to be compared to one another. Example: Average change in PHQ-9 scores of group A (VRBA) was going to be compared to the average change in PHQ-9 scores of group B (BA treatment as usual). The average change in PHQ-9 scores of group A was going to be compared to the average change in PHQ-9 scores of group C (waitlist control). The average change in PHQ-9 scores of group B was going to be compared to the average change in PHQ-9 scores of group C. This change was going to be determined using independent samples t-tests.

However, given the lower-than-expected sample size, in order to assess initial clinical efficacy of the VR BA treatment compared to the BA treatment as usual and control groups, each group's mean as well as each participant's PHQ-9 scores were graphically represented across time. Additionally, each group's mean PHQ-9 change scores from time one through time four were graphically represented.

**Exploratory Aim 1:** To evaluate whether engaging in an activity in VR increases mood more than engaging in an activity in real life.

**Exploratory Aim 1 Analysis:** In order to evaluate whether engaging in an activity in VR increased mood more than engaging in an activity in real life, the differences in mood before

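### The primary hypothesis calls VRBA safe, but safe has no criterion and no planned output reports PHQ-9 item 9, although suicidal ideation is a named, monitored risk

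*SAP*

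**What the plan says.** **The claim.** Protocol section 1.1: "The primary hypothesis of this study is that VR is an acceptable, feasible, and safe way to deliver a BA intervention". The sentences that follow describe acceptability, feasibility and tolerability. The last is narrow: "Tolerability will measure simulator sickness and agitation while using the VR headset". Safety gets no definition.

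**The analysis of that claim.** SAP Aim 1 asks whether VR-delivered BA "is a feasible, acceptable, and tolerable treatment for individuals diagnosed with MDD"; the word safe does not appear. Physical tolerability is measured with the SSQ and emotional tolerability with the BAM, both in relation to the headset. Adverse event rates are tabulated next to dropout, headset use and presence, as barriers to feasibility.

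**The risk.** Protocol section 2.6 excludes people with current suicidal urges and intent. Section 3.1 says of the two treated arms: "If item 9 is endorsed, a risk assessment will be completed in real-time and appropriate actions will be taken". It has a matching rule for the waitlist arm, whose PHQ-9 is given by phone each week for four weeks. Section 4 adds that "suicidal ideation will be assessed each session" and describes safety plans and involuntary holds.

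**The use of the PHQ-9.** Under the SAP's Aim 2 Analysis, "depression scores were measured using the PHQ-9 at four time points". The outputs are group means, individual scores over time and group mean change scores. No item-level output is planned.

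**The concern.** The protocol collects information on suicidal ideation every week in every arm, because the participants are depressed. It also hypothesises that the treatment is safe. The SAP does not connect the two. A team that followed it exactly could describe VRBA as safe on the strength of sickness scores, agitation scores and an adverse event rate with no stated content, while new or worse item 9 responses appeared in no table.

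The SSQ and BAM cannot fill the gap. They measure reactions to the headset, so they do not address ideation and have no counterpart in the BA or waitlist arms. The PHQ-9 plots serve efficacy, and a score for depression as a whole is a poor display of one item. Readers planning the next study would want to know whether ideation emerged on VRBA, and this report could leave them without an answer from data that were already in hand.

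**Working it through.** There is no stated figure to reproduce: the documents give no alpha, power, event rate or safety threshold. The check is a comparison of what is collected with what is reported, followed by illustrative arithmetic.

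**1. Collected against reported**

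| Information | Collected (protocol) | Planned output (SAP) |
|---|---|---|
| PHQ-9 item 9, VRBA and BA | Start of each weekly session (3.1) | None at item level |
| PHQ-9 item 9, waitlist | Weekly by phone, four weeks (3.1) | None at item level |
| Risk assessments, safety plans, holds | Described as clinical actions (3.1, 4) | None named |
| Adverse events | Not defined | A rate, as a feasibility barrier; no by-arm split stated |
| Simulator sickness, agitation | After each VR activity (3.1) | Tables of SSQ and BAM averages and percentages |

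The other SAP outputs are dropout, headset use, presence, technology acceptance, and mood before and after activities. None reports ideation. The SAP does break the SSQ down by item, so item-level reporting is not foreign to the plan.

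**2. Amount of data.** Planned maximum: 10 participants × 4 time points = 40 item 9 responses per arm, and 30 × 4 = 120 in all. The SAP says that the sample was smaller than expected and gives no figure, so the true number is lower.

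**3. Can the planned PHQ-9 outputs hide a change in item 9?** Assumption, not in the documents: nine items, each scored 0 to 3, summed.
- One participant: item 9 goes from 0 to 2 and two other items each fall by 1. Total change = +2 − 1 − 1 = 0, and the individual plot is flat.
- One participant: item 9 rises by 3 and the other eight items each fall by 1. Total change = +3 − 8 = −5, plotted as improvement.
- Arm mean: if 2 of 10 participants worsen by 3 on item 9, the mean moves by 2 × 3 / 10 = 0.6 points.

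These are constructed cases. They show that masking is possible, not how often it would occur.

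**4. What an item 9 table could show.**
- With no events among n participants, the exact one-sided 95% upper bound is 1 − 0.05^(1/n). For n = 10 it is 25.9%; for n = 5 it is 45.1%.
- The chance of at least one case among 10 is 1 − (1 − p)^10. For assumed true rates p of 5%, 10% and 20% it is 40%, 65% and 89%.

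Such a table can therefore list cases, but an empty one rules out little.

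**The case against.** Several stronger readings are tempting, and the documents do not support them.

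- *That SAP Aim 1 tests safety and will return a favourable result.* It does not set out to. Aim 1 and the protocol's stated primary aims speak of tolerability; safe appears in the hypothesis sentence. The defect is that a hypothesised property has no criterion and no analysis. Narrowing the word is a legitimate remedy.
- *That ideation is the main risk the protocol names.* Section 4 does not rank risks. It also mentions confidentiality, psychological effects and motion sickness, and it ties ideation to the depressed population, not to VR. What stands is that ideation is named, checked at each session and has an escalation path.
- *That the report must contain nothing on ideation.* Adverse events are tabulated, and a hold or a new safety plan might be counted there. Nothing requires this and nothing forbids it, so capture is possible but not assured.
- *That the missing table would show whether VRBA is safer or less safe than BA or waitlist.* At this size it could not. The waitlist PHQ-9 is also given by phone while the treated arms complete it at sessions, which weakens a comparison on a sensitive item.

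It is also fair to say that the Aim 2 sentence on the PHQ-9 is sound for efficacy, and that the monitoring of ideation in real time is not in question here. Finally, risk assessments, safety plans and holds are described as clinical actions. The documents do not show that they are logged as study data, so only the item 9 counts can be assumed available. None of this removes the core: item 9 is collected in all arms and no planned output reports it.

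**Conclusion.** The point holds as a gap in reporting. The primary hypothesis claims safety without a criterion; adverse events are undefined; and a named risk, measured weekly in all three arms, has no planned summary. Scores and change scores can conceal a new or worse item 9 response, so the plan could be followed exactly and still leave such responses unreported.

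In size, this is up to 120 planned item 9 responses (fewer in practice) with no summary. One affected participant is about 10% of an arm of 10. The masking examples rest on an assumed 0 to 3 item score and a summed total. Nothing in the documents suggests that ideation did worsen, and no comparative conclusion would be available in any case. It should be corrected, because the safety part of the hypothesis otherwise has no relevant evidence behind it beyond headset tolerability and an undefined event rate.

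**What to change.** Add to SAP Aim 1 a descriptive table by arm (VRBA, BA, waitlist). Because the SAP is written in the past tense, label it as an added safety summary. It should give:

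- the number of participants assessed on item 9 at time 1 and at later time points;
- the number with item 9 endorsed at time 1;
- the number newly endorsed, or worse than at time 1, at any later time point;
- counts of risk assessments, safety plans and holds, where these were recorded.

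State whether these events count as adverse events, and report adverse events by arm. Any statement on safety should cite this table together with the SSQ, the BAM and adverse events. It should say that with about 10 or fewer per arm the evidence is descriptive only (0 of 10 is compatible with a true rate of up to about 26%), and that the waitlist PHQ-9 was given by phone.

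The alternative is to drop safe from the conclusion and limit it to tolerability.

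**Cost:** SAP wording and one small table. The item 9 counts need no new visits or instruments; the counts of clinical actions depend on what was recorded. Small cells need care for confidentiality.

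### Aim 2 compares arms on raw PHQ-9 change without using the time-1 score, so chance baseline imbalance in a small trial shifts the comparison uncorrected

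*SAP*

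**What the plan says.** Protocol 1.1 says the secondary (efficacy) hypothesis will be assessed by "running t-tests comparing the change in PHQ-9 scores at timepoints across the three study arms". The SAP's Aim 2 Analysis makes this specific: "the average change between PHQ-9 scores at time 4 and time 1 for each of the three groups were going to be compared". It lists the three pairwise comparisons and adds: "This change was going to be determined using independent samples t-tests". Neither text gives the time-1 score any role other than as the value subtracted.

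The SAP then says that, because the sample was smaller than expected, graphs were used instead to assess initial efficacy against both comparators. There are two kinds. One shows group means and each participant's PHQ-9 over time. In the other, each group's "mean PHQ-9 change scores from time one through time four were graphically represented".

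On allocation, Protocol 3.1 gives the target size ("A total of 30 participants will be recruited, about 10 participants per study arm") and describes randomisation "using 5 opaque, concealed envelopes in sets of 6 to preserve balance throughout the study". It mentions no stratification by PHQ-9. The achieved sample size is not stated.

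**The concern.** Comparing arms on raw change fixes the slope of the final score on the first at 1. PHQ-9 is measured with error and fluctuates, so the true slope is probably below 1. An arm that happens to start higher then tends to fall further, whatever its treatment. Blocked envelopes balance the number of participants per arm, not their severity, and with 10 or fewer per arm sizeable differences in starting score are ordinary.

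The mean-change graph could therefore favour VRBA because its participants happened to start more depressed, or hide a benefit because they started less depressed. The information needed to allow for this, the time-1 PHQ-9, is already collected.

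**Working it through.** **Is there a figure in the plan to reproduce?** No. The documents give no SD, correlation, effect size or power calculation. The only arithmetic available agrees: 5 sets × 6 = 30, and 30 / 3 = 10 per arm.

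**Inputs.**
- From the documents: three arms, 1:1:1 allocation, 10 per arm planned, fewer achieved.
- Assumed: SD of PHQ-9 = 5 at both times; correlation r = 0.3 to 0.7 (with equal SDs, r is also the slope); 3 to 5 per arm as examples of a shortfall.
- Time 1 is read as the PHQ-9 at the start of session 1, or at the first weekly call in the waitlist arm. The documents do not define it further.

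**Step 1: chance baseline difference between two arms.** SE = SD × √(2/n), and the mean absolute difference is 0.798 × SE.
- n = 10: SE = 5 × √0.2 = 2.24; mean absolute difference 1.78 points.
- n = 4: SE = 5 × √0.5 = 3.54; mean absolute difference 2.82 points.

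**Step 2: shift in the raw-change contrast relative to the adjusted one.** Shift = (1 − r) × baseline difference.

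| r | 10 per arm | 4 per arm |
|---|---|---|
| 0.3 | 0.7 × 1.78 = 1.2 | 0.7 × 2.82 = 2.0 |
| 0.5 | 0.5 × 1.78 = 0.9 | 0.5 × 2.82 = 1.4 |
| 0.7 | 0.3 × 1.78 = 0.5 | 0.3 × 2.82 = 0.8 |

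These treat the slope as known. Simulated three-arm trials with the slope estimated gave 0.54 to 1.22 at 10 per arm and 0.97 to 2.02 at 4 per arm.

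These are averages, not limits. At 10 per arm with SD 4 to 6 and slope 0.3 to 0.7, a 1-SE imbalance shifts the contrast by 0.54 to 1.88 points and a 1.96-SE imbalance by 1.05 to 3.68. With a slope of 0.9, the 1-SE shift is only 0.18 to 0.27.

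**Step 3: direction.** In 40,000 simulated trials with no treatment effect (10 per arm, SD 5, r = 0.5), the mean raw-change contrast was −0.005. The shift goes either way and averages to zero.

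**Step 4: precision.** With a known slope, adjusted variance / raw-change variance = (1 − r²) / [2(1 − r)] = (1 + r)/2. Estimating one common slope from three arms multiplies this by 1 + 1/(3n − 5).

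| n per arm | multiplier | r = 0.3 | r = 0.5 | r = 0.7 | r = 0.8 |
|---|---|---|---|---|---|
| 10 | 1.04 | 0.68 | 0.78 | 0.88 | 0.94 |
| 5 | 1.10 | 0.72 | 0.83 | 0.94 | 0.99 |
| 4 | 1.14 | 0.74 | 0.86 | 0.97 | 1.03 |
| 3 | 1.25 | 0.81 | 0.94 | 1.06 | 1.13 |

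Simulation agrees closely (0.78 at 10 per arm and 0.86 to 0.87 at 4 per arm, r = 0.5).

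**Step 5: how much of the interval gain is due to adjustment?** Mean 95% half-widths for pairwise raw change, raw change with error pooled over three arms, and the adjusted model:
- 10 per arm, r = 0.5: 4.61, 4.53, 4.01. Most of the gain is adjustment.
- 4 per arm, r = 0.5: 8.35, 7.81, 7.30. About half is pooling.
- 4 per arm, r = 0.7: 6.41, 6.01, 5.98. Nearly all is pooling.
- 4 per arm, r = 0.8: 5.25, 4.90, 5.04. Adjustment is slightly worse than pooled raw change.

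**The case against.** The t-tests are an abandoned plan. The current Aim 2 specifies no test, interval or numerical contrast, so no stated efficacy estimate is there to be moved. The SAP also plots group means and every participant's scores over time, so a reader can see any baseline gap beside the change graph. Efficacy is a secondary, exploratory aim of a feasibility study. The shift is small beside half-widths of 4.6 points (10 per arm) or more, so no contrast at this size would be conclusive either way. A model at very small n would also bring back what the SAP dropped for lack of numbers.

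Most of this stands, and it limits the point. What remains is that the SAP still uses the mean-change graph to assess efficacy between arms. That graph takes the baseline level out of view, and the companion plots do not tell a reader how much of a change difference the baseline gap explains.

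A reader might infer that raw change makes the efficacy comparison biased. The documents do not support that: allocation is randomised, and raw change is unbiased on average. A reader might also infer that the result is known to be off by 0.5 to 2 points. It is not: the SD, the correlation and the achieved sample size are all missing from the documents. Nor does adjustment always sharpen the estimate; steps 4 and 5 show that it may not at 3 or 4 per arm.

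**Conclusion.** The point holds in limited form. The planned tests and the graph that survives them both compare arms on change that is not adjusted for the starting score, in a trial too small to rely on randomisation to even out PHQ-9. Given the baseline difference that actually occurred, the contrast is shifted in one direction or the other, by about 0.5 to 1.2 points on average at 10 per arm and about 1 to 2 points at 4 per arm. These sizes rest on an assumed SD of 5 and correlation of 0.3 to 0.7, and they shrink quickly if the slope is near 0.9. The existing plots let a reader detect the imbalance but do not remove its effect. The problem is conditional error and, at about 10 per arm, lost precision. It is not systematic bias, and it bears on a secondary aim only.

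**What to change.** In the SAP's Aim 2 Analysis:
- Wherever a between-arm PHQ-9 contrast is reported, take it from one linear model of time-4 PHQ-9 on arm (all three) and time-1 PHQ-9, and give its interval. The SAP is written in the past tense, so label such an analysis as added after the fact if the data have already been examined.
- Show the time-1 arm means beside the mean-change graph, and label raw change as descriptive.
- If the arms are too small to estimate the slope (roughly 4 or fewer each), fit no model and plot time 4 against time 1 by arm.
- Bring the wording in Protocol 1.1 into line.

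The cost is some SAP wording, a few lines of code and one degree of freedom, with no new data. At 10 per arm the variance falls to about 0.7 to 0.9 of that of raw change under the assumed correlations. At 3 to 4 per arm with a correlation of 0.7 or more there is no useful gain and possibly a small loss, which is why the last resort is a plot and not a model.

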acceptance, as labeled on the scale, the average score was then scaled back depending on the number of questions. For example, the “Perceived Usefulness” category included three questions, yielding a potential range of 0 to 12, so an average score of 10 would be divided by 3 to assess the degree of acceptance (in this case it would yield a score of 3.33, which would correlate to “agree” on the Likert scale). Physical tolerability of the VR headset was assessed by participant report using the SSQ, and the emotional tolerability of the VR headset was assessed by participant report using the BAM, again represented in tables. Physical tolerability was broken into each item and ranged from 0 (no more than usual) through 3 (severely more than usual) for each item. Each participant’s scores were averaged and placed into a table, along with the average ITT participants and protocol completers’ scores. The total percentage tolerability rating for a given activity was calculated by dividing a participant’s score by 48, since there were 16 items, yielding a potential range of 0 to 48. For example, if a participant endorsed *nausea* slightly more than usual (1), *sweating* moderately more than usual (2), and *headache* slightly more than usual (1) during the VR activity labeled “Puppies,” then his/her percentage score would be calculated by dividing 4 by 48, to yield 8.33% intolerability or 91.67% tolerability during that activity. The percentage of intolerability for each symptom category was similarly calculated by dividing the average score by the maximum potential score of 3. The average scores for physical tolerability were summed for each participant and placed into a table, along with the average emotional tolerability scores of each participant. Emotional tolerability was scored from 1 (strongly disagree) to 7 (strongly agree) per question; and with three questions, there was a possibility of yielding a score between 3 and 21. These scores were rescaled to a range of 0 to 18 by subtracting 3 from all scores. The percentage of physical intolerability and

emotional intolerability were calculated by dividing the average scores by the highest potential score (48 for physical tolerability and 18 for emotional tolerability).

**Aim 2:** To assess whether VR BA is efficacious in treating the symptoms of MDD compared to BA as usual or a waitlist control.

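### With the sample short, the SAP meets its comparative PHQ-9 aim with plots alone and specifies no between-arm difference or measure of its uncertainty

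*SAP*

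**What the plan says.** The SAP states Aim 2 as "To assess whether VR BA is efficacious in treating the symptoms of MDD compared to BA as usual or a waitlist control". Its Aim 2 Analysis first describes what had been intended: "the average change between PHQ-9 scores at time 4 and time 1 for each of the three groups" would be compared, giving three pairs (VRBA v BA, VRBA v waitlist, BA v waitlist). On the method it says: "This change was going to be determined using independent samples t-tests".

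The next paragraph describes what replaced this: "given the lower-than-expected sample size, in order to assess initial clinical efficacy" of VRBA against both comparators, each group's mean and each participant's "PHQ-9 scores were graphically represented across time". In addition, each group's "mean PHQ-9 change scores from time one through time four were graphically represented".

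Protocol section 1.1 sets the weight of the aim: "The secondary aim of this study is to explore the efficacy of using VR to deliver BA therapy to a clinical MDD population". It also states a direction: "A secondary hypothesis is that VRBA will have stronger effects than BA treatment as usual or a waitlist control". The only analysis it names for this hypothesis is t-tests on PHQ-9 change across the arms.

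**The concern.** The aim and the stated purpose of the plots are comparative, but the replacement analysis produces only within-arm displays. A small sample is a good reason to give up significance tests. It is not a reason to leave out the estimate and its precision, because uncertainty is largest when n is small.

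The hypothesis has a direction, so readers will look for a gap between the plotted means in favour of VRBA. The group-mean plots show such a gap with nothing specified to say how imprecise it is. What is at stake is how an early efficacy signal from this trial is read, not a confirmatory conclusion.

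**Working it through.** **1. Is an estimate specified anywhere?** The finding rests on the text.

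- SAP, Aim 2: comparative question.
- SAP, Aim 2 Analysis, intended plan: three pairwise t-tests, no interval mentioned, described as what was going to be done.
- SAP, Aim 2 Analysis, as carried out: plots of group means, individual scores and group mean changes.
- Protocol 1.1: t-tests only.

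Neither document specifies a between-arm difference, standard error or interval for Aim 2 as carried out. A crude difference could be read off the mean-change plot, but not its uncertainty.

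**2. Inputs for an illustration.** From the documents: 30 participants, 1:1:1 allocation, so 10 per arm; the envelope scheme agrees (5 × 6 = 30). Not in the documents: achieved n, SD of PHQ-9 change, alpha and power. There is therefore no figure of the plan's own to reproduce. Assumed: SD of change 5 points (range 4 to 6), equal arms, two-sided 95%, and 4 or 6 per arm as examples of a shortfall.

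**3. Was dropping the tests reasonable?** Two-sided 5% t-test, noncentrality d × √(n/2). At 10 per arm and d = 0.5 this is 0.5 × 2.236 = 1.118, power about 19%. At d = 0.8 it is 1.789, power about 40%. At an assumed 5 per arm, power is about 11% and 20%. Dropping the tests is understandable.

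**4. How wide would an interval be?** Equal-variance half-width = t(0.975, 2n−2) × SD × √(2/n).

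| n per arm | t | SD × √(2/n), SD 5 | Half-width, SD 5 | SD 4 to 6 |
|---|---|---|---|---|
| 4 | 2.447 | 3.536 | 8.7 | 6.9 to 10.4 |
| 6 | 2.228 | 2.887 | 6.4 | 5.1 to 7.7 |
| 10 | 2.101 | 2.236 | 4.7 | 3.8 to 5.6 |

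**5. Does the Welch form hold up at very small n?** Simulated mean half-widths, normal data, true SD 5 in both arms, no effect:

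| n per arm | Welch | Equal variance |
|---|---|---|
| 2 | about 35 | 19 |
| 3 | 12.4 | 10.7 |
| 4 | 8.9 | 8.3 |

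The equal-variance mean of 8.3 at 4 per arm is below the 8.7 in step 4 because it uses estimated SDs, which average below the true value in small samples. The cost of Welch is small at 4 per arm but large at 2.

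**6. Three unadjusted intervals.** In simulation with no true effect and equal SDs, at least one of the three Welch intervals excludes zero in 10.3%, 11.4% and 11.9% of trials at 4, 6 and 10 per arm. This is why a label ruling out efficacy claims is needed.

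**The case against.** The strongest reply is that the SAP already discloses most of the information. It plots every participant's scores, so a reader who can follow the individual lines can recover the changes, their SD and an interval. With a handful of participants, showing all the data is a defensible choice. This largely stands. A reader might infer that the plots leave no way to judge how large a gap chance could produce; the documents do not support that, because individual scores are shown. What remains is that the imprecision of a difference is not stated and has to be worked out by the reader.

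Second, efficacy is secondary and exploratory, the SAP speaks only of initial efficacy, and it gives its reason for the change. This also stands, and it keeps the weight low. A reader might infer that the SAP claims VRBA works, or conceals the change of analysis. It does neither.

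Third, the numbers are not this trial's: achieved n and SD are assumed. That is correct. They show scale only, and the gap in the text does not depend on them.

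Fourth, intervals could be uninformative at the smallest sizes, and limiting them to participants with both scores ignores dropout. Both points are right, and the fix takes them in.

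**Conclusion.** The point holds as a minor gap in estimation and reporting. Aim 2 remains comparative, the planned contrasts were replaced by plots, and neither document supplies a between-arm PHQ-9 difference or its uncertainty. On the assumptions in the working (SD of change 4 to 6, equal arms, equal-variance formula), a single difference would carry a 95% half-width of about 7 to 10 points at 4 per arm and about 4 to 6 at the planned 10. The imprecision is therefore worth stating outright.

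The documents do not support the stronger conclusion that the efficacy results are invalid or that the t-tests should have been kept. The tests would have had low power even at full recruitment for the standardised differences examined (0.5 and 0.8), and the SAP draws no inferential conclusion from the plots.

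**What to change.** Keep the plots and add one short table to the Aim 2 Analysis:

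- For each arm: number randomised, number with both time 1 and time 4 PHQ-9 scores, and mean and SD of change.
- The three originally planned pairwise differences in change, each with a Welch 95% interval, labelled post hoc, exploratory, unadjusted for multiplicity and carrying no efficacy claim.
- A statement that this is a completer analysis that does not address dropout, with dropout by arm beside it. The SAP already reports both intention-to-treat and completer averages for Aim 1, so the restriction should be visible here too.
- Where an arm has only two or three participants with both scores, list the individual changes and treat that comparison as descriptive. With fewer than two, state that no interval can be estimated.

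If no intervals are reported, leave Aim 2 as written and state that the between-arm comparison could not be assessed. Rewording the aim after the data were seen would blur a departure that the SAP now discloses.

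The cost is a few lines of SAP text and a small calculation on scores already collected. The downside is wide intervals, which will show that the data cannot settle the efficacy question.
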